7.2 PARTICIPANT DISCONTINUATION/WITHDRAWAL FROM THE STUDY

Participants are free to withdraw from participation in the study at any time upon request.

An investigator may discontinue a participant from the study for the following reasons:

- Significant study intervention non-compliance, i.e. inability or unwillingness to complete study intervention or outcome assessments
- Lost-to-follow up; unable to contact subject (see **Section 7.3, Lost to Follow-Up**)
- Any event or medical condition or situation occurs such that continued collection of follow-up study data would not be in the best interest of the participant or might require an additional treatment that would confound the interpretation of the study
- The participant meets an exclusion criterion (either newly developed or not previously recognized) that precludes further study participation
- The study is suspended or canceled

The reason for participant discontinuation or withdrawal from the study will be recorded on the Case Report Form (CRF). Subjects who sign the informed consent form and are randomized but do not receive the study intervention may be replaced. Subjects who sign the informed consent form, and are randomized and

receive the study intervention, and subsequently withdraw, or are discontinued from the study, will be replaced.

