Eighteen RMT subjects in the parent study will be recruited to our CBT+CCT group, and thirty-six age- and gender-matched CBT subjects in the parent study will be recruited to our CBT control group. The proposed study may add:

- 1) For all fifty-four subjects recruited from parent study:
 - a. NIH Toolbox and/or Millisecond behavioral assessment before and after the CBT course of therapy as well as once before the RMT course of treatment and once at about 3 weeks of CBT and another time if completing the fMRI following 4 weeks of at home CCT for the CBT+CCT group
 - b. BRIEF2 questionnaire before, after, and at about week 3 of the CBT course of treatment, as well as once before the RMT course of treatment and at the fMRI following 4 weeks of at home CCT for the CBT+CCT group
 - c. Clinical assessment of anxiety at week 3 of CBT treatment.
- 2) For patients originally randomized to RMT in the parent study who wish to enroll in the current study during their Optional CBT participation:
 - a. augmentation of the CBT offered by the parent R01 study with CCT games delivered prior to each CBT session (CBT+CCT) along with a brief survey (the Self-Assessment Manikin) they may be asked to complete before and after CCT
 - b. fMRI following 4 weeks of at home CCT, and fMRI following CBT+CCT completion
 - c. Clinical measures and assessments before and throughout the course of CBT treatment
 - d. at home CCT (~30 min/day), 5x per week, for up to 4 weeks, for up to two weeks before starting CBT and for up to 4 weeks after starting CBT, along with a brief survey (the Self-Assessment Manikin) they may complete before and after CCT

Data analyses will compare pre- and post-CBT data from the parent study with pre- and post-CBT+CCT data collected for the proposed study. These data will include NIH Toolbox and/or Millisecond measures of behavioral capacity for cognitive control; multi-modal assessment of TCN with fMRI, resting state and DTI; and, detailed assessment of anxiety symptoms using both clinician-interview and self-report. Pre- to post-therapy change in anxiety severity (clinician-measured) will serve as the primary outcome variable; regression analyses will be used to test for associations of anxiety change with changes in brain-behavioral indices of cognitive control following CBT compared to CBT+CCT. To increase clinical relevance of study results, analyses will also consider responder status, a common end point for clinical trials.

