5 STUDY POPULATION

Fifty-four clinically anxious youth will be studied (36 CBT, 18 CBT+CCT). All subjects will be between 7 and 17.99 years old at the time of initial consent. Subjects will be recruited from an existing R01 study at the University of Michigan (HUM00118950, PI [name]), also referred to as parent study. The R01 parent study, at year 4 of the five-year period, has successfully recruited and retained over 100 anxious youth with moderate or greater levels of symptoms, e.g., PARS score > 10 and CGAS score < 60; it will recruit over 100 additional anxious youth randomized 2:1 to CBT and RMT through 05/31/2021. To date, nearly all participants randomized to RMT in the parent R01 study have chosen to continue the CBT sessions after RMT completion; thus we expect 44 youth to be eligible for the CBT+CCT, providing ample opportunity to recruit 36 CBT and 18 CBT+CCT over the one year period of the proposed study. Based on the retention rates of therapy (96.2%) and fMRI motion (89%) in the parent R01, we expect to have 32 CBT-treated and 14 CBT+CCT-treated anxiety youth with usable pre- and post-treatment data.

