6.3 MEASURES TO MINIMIZE BIAS: RANDOMIZATION AND BLINDING

There is no randomization in this pilot study. Participants are recruited from the parent study where assignment to the two treatment arms (CBT vs RMT) is stratified based on age and gender, using block randomization to ensure a 2:1 ratio of participants in CBT vs. RMT group (HUM00118950). In this study, we will recruit all possible participants in the RMT group in the parent study to participate in CBT+CCT, and recruit age- and gender-matched participants from CBT group. Efforts will be made to keep therapists blinded to participant group (i.e., CBT+CCT vs. OPT CBT).

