9 STATISTICAL CONSIDERATIONS

9.1 STATISTICAL HYPOTHESES

- Primary Endpoint(s): Change in Brain activation and connectivity in the task-control network (TCN)

We hypothesize that **(a)** both groups will have increased activation and functional connectivity in task-control network after therapy vs. before therapy; however, **(b)** the increase will be greater in CBT+CCT vs. CBT only group. Baseline and week 12 assessment will evaluate pre- to post-CBT changes in brain activation and function connectivity in the task-control network including fronto-parietal and cingulo-opercular regions mediating cognitive control. Functional activation and connectivity of these brain regions are assessed using a conflict interference computer task performed during MRI scanning.

- Secondary Endpoint(s):
 - (1) Change in behavioral performance on the conflict interference task and tasks testing cognitive control capacity included in the NIH Toolbox: We hypothesize that **(a)** both groups will have improved behavioral performance on the conflict interference task and tasks testing cognitive control capacity included in the NIH Toolbox; however, **(b)** these effects will be greater in CBT+CCT vs. CBT group. This will be evaluated using two measures of the same construct at baseline and week 12. Pre- to post-CBT changes in the behavioral performance in a conflict interference task will be collected, as well as composite score from tasks included in the NIH toolbox.
 - (2) Change in Pediatric Anxiety Rating Score (PARS): We hypothesize that relative to CBT group, anxiety severity will be reduced more and treatment response rate will be higher in CBT+CCT group. This will be evaluated at baseline and week 12 through the PARS, a 50 question interview-based tool used to assess for the presence and severity of anxiety symptoms in children and adolescents utilizing parental and youth input to guide clinician ratings. The total scores on this scale range from 0 to 30, with scores above 13 indicating clinically meaningful anxiety.

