9.3.3 ANALYSIS OF THE SECONDARY ENDPOINT(S)

- (1) We hypothesize that CCT will increase cognitive control capacity (measured by NIH toolbox CC composite scores and behavioral performance on the MSIT task and/or Millisecond scores). The hypothesis will be tested using 2 (within-subject: pre vs. post) x 2 (between-subject: CBT vs. CBT+CCT) repeated-measures ANOVAs on behavioral performance.
- (2) Repeated-measure ANOVAs will be conducted to examine effect of CCT on CBT. We hypothesize that anxiety severity (i.e., continuous PARS score) will be reduced more in CBT+CCT group, relative to CBT group. Chi-square tests will be used to test for differences in the ratio of CBT responders: non-responders between CBT+CCT and CBT group. We hypothesize that CBT+CCT will have more responders than the CBT.

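### The PARS analysis drops anyone without a week-12 rating, and the plan does not say that withdrawn and replaced participants stay in it; a mixed model on the ratings already scheduled would keep them

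*Combined protocol and SAP*

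**What the plan says.** Section 7.2 covers treated participants who leave: those who "receive the study intervention, and subsequently withdraw, or are discontinued from the study, will be replaced". It also requires the reason for leaving to be recorded. It does not say what happens to the data already collected.

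For anxiety severity, section 9.3.3 states: "Repeated-measure ANOVAs will be conducted to examine effect of CCT on CBT". It lists no time levels. Section 9.1 supplies them: "This will be evaluated at baseline and week 12 through the PARS". Section 4.1 points the same way: "Data analyses will compare pre- and post-CBT data from the parent study with pre- and post-CBT+CCT data collected for the proposed study". Section 9 names no analysis population and no method for missing data.

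Sections 6.4 and 8.2 schedule independent PARS ratings at weeks 0, 1, 3, 6, 9 and 12. Section 7.1 continues outcome assessments, where possible, after treatment is stopped on its criteria.

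On expected losses, section 5 says: "Based on the retention rates of therapy (96.2%) and fMRI motion (89%) in the parent R01", the plan expects "32 CBT-treated and 14 CBT+CCT-treated anxiety youth with usable pre- and post-treatment data".

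**The concern.** A two-point repeated-measures ANOVA can use only participants who have both ratings. A treated child who leaves at week 6 contributes nothing, even with four PARS ratings on file. If section 9.3.3 means a classical ANOVA on all visits, the loss is larger: anyone missing any rating drops out, and section 8.2 tolerates a missed week 9.

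Some routes out of the study follow a poor course. Section 2.3.1.1 allows withdrawal after symptom worsening. Sections 5.3 and 6.5.1 withdraw participants who start other medication, and 6.5.1 those who need more than the limited extra sessions. If such exits were commoner in one group, a completer comparison would flatter that group.

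Two features raise the stakes. The CBT+CCT group has only 18 participants, so each one omitted is 1/18 = 5.6% of it. Section 9.2 also says the pilot is meant to supply effect sizes for the next grant application, so any distortion would be carried forward. PARS is listed as secondary in section 9, but section 4.1 treats clinician-measured anxiety change as the main outcome variable.

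**Working it through.** **1. The plan's own figure.** Expected usable = n × retention × usable-motion rate.
- CBT: 36 × 0.962 × 0.89 = 30.8 (stated 32)
- CBT+CCT: 18 × 0.962 × 0.89 = 15.4 (stated 14)
- Total: 54 × 0.962 × 0.89 = 46.2 (stated 46)

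The total reproduces, and each group is within two participants. These figures include fMRI motion, so they do not measure PARS loss.

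**2. Loss relevant to PARS.** Therapy loss is 1 − 0.962 = 3.8%: 36 × 0.038 = 1.4 in CBT and 18 × 0.038 = 0.7 in CBT+CCT, or 54 × 0.038 = 2.05 in all.

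**3. Why the ANOVA drops them.** In a 2 × 2 pre/post ANOVA the group-by-time interaction is the two-sample test on week 12 minus baseline. Without week 12 there is no difference score.

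**4. Size of a shift.** Let G be how much worse the change is in those lost than in those kept. The mean change among those kept is the full mean minus p × G, so the contrast (CBT+CCT minus CBT) moves by −(p1 − p0) × G. A negative value favours CBT+CCT. The documents give no PARS SD or correlation, so G comes from a simulation with no true effect. Its assumptions are n = 36 and 18, mean 17 falling to 11 in both groups, SD 4 rising to 5, correlation 0.75 or 0.85 per 3 weeks, and leaving after week 3, 6 or 9. If leavers come from the third with the worst change so far, G is 3.1 to 3.7 points:
- 10% vs 3.8%: 0.062 × 3.1 = 0.19 to 0.062 × 3.7 = 0.23
- 20% vs 3.8%: 0.162 × 3.1 = 0.50 to 0.162 × 3.7 = 0.60

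Simulated shifts of the completer ANOVA, in PARS points:

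| Loss, CBT+CCT vs CBT | Worst third leave, none rated later | Same, half still rated at week 12 | Odds of leaving double per SD of worse change, none rated later |
|---|---|---|---|
| 3.8% vs 3.8% | within 0.02 | not run | not run |
| 10% vs 3.8% | −0.20 to −0.23 | −0.11 | −0.13 |
| 20% vs 3.8% | −0.55 to −0.62 | −0.28 | −0.39 |
| 0% vs 3.8% | +0.15 to +0.17 | not run | not run |

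Under the harshest of the three rules (worst third, none rated later), the shifts for 10 to 20% loss are 0.14 to 0.39 of the contrast's standard error (1.37 to 1.69). A second simulation with other assumptions (SD 4, graded dropout after week 3, 5% loss in CBT and 20% in CBT+CCT) gave −0.22 for completers, +0.04 for likelihood analysis and +0.01 for full data.

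**5. What the mixed model does.** In the worst-third scenarios a likelihood model on all visits, fitted without covariates, stays within 0.04 of zero. If leaving depends on the unseen week-12 change instead, it keeps about 57% of the bias (0.19 to 0.62 points, against 0.33 to 1.07 for the ANOVA). If the worsening comes only after the last rating, it keeps all of it.

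**6. Administrative loss.** With random loss of 20% vs 3.8% neither method is biased. The SD of the contrast is 1.66 for the ANOVA against 1.61 for the mixed model (1.40 against 1.36 at the higher correlation).

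**The case against.** The best defence is that little is lost. On the documented retention the effect is about 2 of 54 children, and between-group bias is near zero if loss is alike. That stands. The CBT+CCT group also comes from participants who finished RMT and chose to go on (section 4.1), so it may already be selected for retention and could lose fewer. That stands too: the direction is open. Section 7.1 keeps rating participants after treatment is stopped, where possible, which roughly halves the shift if half the leavers are rated. An unstructured covariance over six visits has 6 × 7 / 2 = 21 parameters for 54 children, so a simpler fallback is needed.

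Four stronger readings are tempting, and the documents do not support them.
- **Replacement means removal from the analysis.** Section 7.2 is a recruitment rule and removes nobody by itself. The gap is the silence of section 9.
- **The expected 32 of 36 and 14 of 18 show heavier loss in CBT+CCT.** The stated rates are common to both groups, give 1 − 0.962 × 0.89 = 14.4% in each, and include scanner motion.
- **CBT+CCT participants are at risk for longer, about 14 weeks against 12.** At-home CCT is optional, and section 8.2 lets sessions run to 16 weeks, so the ranges overlap.
- **The word randomized in section 7.2 contradicts section 6.3** ("There is no randomization in this pilot study"). It can naturally mean the parent study's randomization, which section 6.3 describes.

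**Conclusion.** The point holds as an inexpensive improvement that should be made; it is not a demonstrated bias. The PARS analysis as planned discards treated participants who lack week 12, and nothing says that replaced participants are kept. On the documents' own retention this is about 2 of 54, with negligible between-group bias under equal loss. A shift of roughly 0.1 to 0.6 PARS points needs unequal, outcome-related loss of the assumed size (10 to 20% against 3.8%). Within that range it depends on how strongly leaving follows the observed course and on how many leavers are still rated. No CCT-specific retention is given. A reader might infer that the plan builds in a false benefit for CCT; the documents show neither unequal loss nor its direction, and the sign reverses if CBT+CCT loses fewer. Loss because funding ends (section 10.2, version 7.0 rationale) would cost precision without biasing the PARS contrast.

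**What to change.** In section 9.3.3:

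1. State that everyone who starts a first CCT or CBT session is analysed in their group, including those later withdrawn and replaced. A change of model does not secure this by itself.
2. Replace the PARS ANOVA with a likelihood-based linear mixed model on all available scheduled PARS ratings: group, categorical visit, group-by-visit, and the matching variables age and gender. Use unstructured covariance, with a named simpler structure if it does not converge, and small-sample degrees of freedom such as Kenward-Roger. Report the group difference in baseline-to-week-12 change with its interval.
3. State that the model assumes dropout depends on observed ratings. Add a sensitivity analysis in which withdrawn participants do worse at week 12 than predicted, for example by 2 and 4 points. At the assumed loss differences this moves the contrast by 0.062 × 2 = 0.12 to 0.162 × 4 = 0.65 points.
4. Report withdrawals and replacements by group and recorded reason.

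The cost is plan wording and slightly more analysis work; no new assessments are needed. The main PARS result then relies on missing at random, and the model does not remove bias if dropout depends on ratings nobody saw. A participant with only a baseline rating will still add almost nothing to the change contrast.

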7.3 LOST TO FOLLOW-UP

A participant will be considered lost to follow-up if he or she fails to return for four scheduled visits and study staff are unable to contact the participant after at least 3 attempts for each visit.

The following actions must be taken if a participant fails to return for a required study visit:

- The experimenter will attempt to contact the participant, reschedule the missed visit within four weeks, counsel the participant on the importance of maintaining the assigned visit schedule and ascertain if the participant wishes to and/or should continue in the study
- Before a participant is deemed lost to follow-up, the experimenter designee will make every effort to regain contact with the participant (where possible, 3 telephone calls and emails). These contact attempts will be documented in the participant's study file.
- Should the participant continue to be unreachable, he or she will be considered to have withdrawn from the study with a primary reason of lost to follow-up.

8 STUDY ASSESSMENTS AND PROCEDURES

8.1 ENDPOINT AND OTHER NON-SAFETY ASSESSMENTS

8.1.1 SCREENING AND INITIAL ASSESSMENTS

Participants will complete questionnaires in order to collect basic health and demographics information. The initial assessment is completed as part of the parent study and will occur in 1 – 3 sessions, depending upon subject convenience. Data collected from this assessment will be used for analysis for this protocol. The following evaluations and assessment tools (or subsets of questions from these measures) may be used to determine eligibility for the study and gather baseline information:

- 1) Demographics and medical history form. An in-house form for basic demographic information, medical and family history completed by study team or as self-report.
- 2) Social Communications Questionnaire (SCQ) (Rutter et al, 2003). A 40-item parent report to rule out diagnosis of Autism Spectrum Disorder.
- 3) Child Behavior Checklist (CBCL), (Achenbach and Rescorla 2001). A 126-item parent-completed checklist which provides DSM-IV oriented subscales for Depressive Problems, Anxiety Problems and Attention Deficit/Hyperactivity Problems (Inattention and Hyperactivity/Impulsivity subscales). Approximately 10 minutes.
- 4) Beck Anxiety Inventory (BAI; Beck & Steer, 1993). This 21-item self-report survey measures severity of anxiety symptoms in adolescents and adults. Approximately 5 minutes.
- 5) Beck Depression Inventory-II (BDI; Beck, Steer, & Brown, 1996). 21-item self-report measure assessing adult depression. Approximately 5 minutes.
- 6) Family Accommodation Scale (FAS; Lebowitz et al., 2012): 13-item parent report measure assessing family accommodation of child symptoms. Approximately 5 minutes.

- 7) Screen for Child Anxiety Related Disorders (SCARED Parent and Child Versions): Developed by [name]., [name]., Marlane Cully, M.Ed., [name]., and [name]., Western Psychiatric Institute and Clinic, University of Pittsburgh (October, 1995). The SCARED consists of 41 items and 5 factors that parallel the DSM-IV classification of anxiety disorders.
- 8) Tanner stage will be determined by self-report on the Pubertal Development Scale (PDS) (Petersen, Crockett et al. 1998).
- 9) Edinburgh Handedness inventory (Oldfield, 1971). A 15-item self-report of hand use.
- 10) State-Trait Anxiety Inventory for Children (STAII-C); (Spielberger, 1973). A self-report, 20-item scale on anxiety symptoms (trait only) for child subjects. Approximately 5-10 minutes.
- 11) Obsessive-Compulsive Inventory (OCI) (Foa, Huppert et al. 2002). An 18-item self-report scale for OC behavior, from normal to pathological. Total scores on this scale range from 0 to 72, with scores above 21 indicating a likely OCD diagnosis. Approximately 10 minutes.
- 12) Multidimensional Anxiety Scale for Children (MASC); (March, Parker et al. 1997). Self-report assessing anxiety. Approximately 10-15 minutes.
- 13) Children's Depression Inventory (CDI); (Kovacs, 1992). Self-report, 28 item scale on depressive symptoms. Approximately 5 minutes.
- 14) Pediatric Anxiety Rating Scale (PARS). A clinician-administered assessment to rate the severity of anxiety symptoms associated with common DSM-V anxiety disorders (social phobia, separation anxiety disorder, and generalized anxiety disorder) in children. Total scores on this scale range from 0 to 30, with scores above 13 indicating clinically meaningful anxiety. Approximately 20–30 minutes.
- 15) Clinical Global Impressions-Severity and Improvement Scale (CGI-S/I); (Guy and Bonato 1970).
- 16) Children's Global Assessment Scale (CGAS); (Shaffer, Gould et al. 1983). A single-item scale, administered by the clinician.
- 17) Columbia Suicide Severity Rating Scale, present/lifetime version (Posner, Oquendo et al. 2007). A clinician-rated scale assessing suicidal ideation and behavior. Approximately 5 min.
- 18) Kiddie Schedule for Affective Disorders and Schizophrenia (K-SADS); (Kaufman, Birmaher et al., 1997). Standard assessment tool to obtain a diagnosis, may include parent interview. Approximately 3-4 hours.
- 19) Grit Scale: (Duckworth, 2007): 12 item measure. Add up all the points and divide by 12. The maximum score on this scale is 5 (extremely gritty), and the lowest scale on this scale is 1 (not at all gritty).
- 20) Life Events Checklist: Adapted from Child and Adolescent Survey of Experiences: Child Version (CASE) (Allen and Rapee, 2009). Assessing events people may find bad or upsetting, as well as events people may find good or enjoyable. Approximately 15 minutes.
- 21) Wechsler Abbreviated Scale of Intelligence (WASI). A short-form administration of two sub-tests of the WAIS (vocabulary and matrix design) to establish IQ. 15 min (can be completed at any time prior to fMRI #2).
- 22) fMRI Safety Screen form to ensure that there are no contraindications for fMRI. This form is provided by the fMRI lab and is not included within study documentation. The most current version of this screening form will be used at all times to ensure the safety of participants undergoing fMRI.

Electronic data capture:

Subjects may complete the self-report forms described above using Qualtrics or hardcopy forms. Qualtrics is an Application Service Provider (ASP) with a Software-as-a-Service (SaaS) platform for creating and distributing online surveys and related research services. The platform records response data, performs analysis, and reports on the data. All services are online and require no download software; only modern JavaScript-enabled browsers are required (no Java/JVM or Flash). Surveys are usually taken online within

a web browser, with optional SMS surveys and offline methods available for smartphones/tablets. Qualtrics has been approved for the University of Michigan research community, and individual investigators access the web interface through a University of Michigan Qualtrics portal. Subjects may receive a coded link via email which will take them to the required surveys. The emailed link contains no identifiable information about the subjects, and once activated, establishes an https encrypted link with the Qualtrics server. Once completed, each survey is locked so that re-access is not permitted. We can also adapt the process for each subject, e.g. provide access on computers or tablets in the Department of Psychiatry for subjects who do wish or cannot use email. Some subjects may request paper, and, if so, paper forms will be provided.

If desired, subjects can receive the initial assessments either in hard copy or an emailed link ahead of attending their initial assessment to limit their time on site. Subjects will be asked to complete the online Qualtrics survey prior to their initial evaluation. A copy of the consent form will be emailed to the subject, along with a secure web-link to the Qualtrics site or a copy of the consent form included in the hard copy packet. For this, a waiver of documentation of informed consent will be sought. If subjects who complete these online surveys screen out, their Qualtrics data will be deleted. Data will be downloaded from Qualtrics and secondarily stored in a REDCap database to be used for analysis.

Responses entered by subjects will be available to the clinicians working with the patient subjects in the study. Please note that the suicide assessment rating (C-SSRS) is administered by clinicians at every visit. Thus, any potentially dangerous clinical condition will be identified in a timely fashion and acted upon accordingly.

